#### 1. Introduction

#### 1.1 Background

Mitochondrial dysfunction has been implicated in aging as well as multiple diseases, including heart failure. Multiple dietary supplements aim at improving mitochondrial function, often without clear evidence of efficacy. In myocardium, mitochondrial dysfunction is characterized by increases in both the NADH/NAD+ ratio and mitochondrial protein acetylation. Recently, we have demonstrated in mice that intraperitoneal administration of nicotinamide mononucleotide (NMN), an NAD+ precursor, can increase myocardial NAD+ levels and normalize the NADH/NAD+ ratio, decrease mitochondrial protein acetylation, and protect against pressure overload-induced cardiac dysfunction.

Though NMN is not orally bioavailable, we and others have shown that oral supplementation with nicotinamide riboside (NR), the precursor from which NMN is produced, also decreases (normalizes) tissue NADH/NAD+ ratio and improves mitochondrial function in mouse models. These animal model results suggest a conceptually innovative mechanism linking mitochondrial dysfunction to the development and progression of heart failure that is distinct from the existing hypotheses of oxidative stress and energy starvation. We hypothesize that oral supplementation with NR will increase NAD+ levels, thereby normalizing the NADH/NAD+ ratio caused by mitochondrial dysfunction during chronic stresses, and improve functional capacity and ventricular function in systolic heart failure.

We have data suggesting that NR is safe and well-tolerated at a dose of up to 1000mg twice daily in humans:

- 1.1.1. We have completed an NIH-funded study of NR pharmacokinetics in 8 healthy volunteers, in which NR was up-titrated to a dose of 1000mg twice daily by Day 7. NR appeared to be safe and well-tolerated in this Study (Airhart PLOS ONE, 2017). Whole blood NAD+ levels increased by a mean of 100%
- 1.1.2. We currently are performing a safety and tolerability trial of NR in 30 participants with clinically-stable, systolic heart failure. In this Study, patients are randomized 2:1 to NR vs. placebo and followed on randomized Study drug for 12 weeks. Patients receive NR at 1000mg twice daily for the final 9 weeks of the Study. to date, 25 participants have completed the Study. While we, as investigators, are therefore still blinded to Study results, the Study's Data Safety and Monitoring Committee (DSMC) has completed interim reviews Study results after completion of 10 and then 20 participants. Following each interim review, the DSMC recommended Study continuation.
- 1.1.3. In a 2x6-week double-blind crossover study of NR at a lower dose of 500mg BID, NR was well-tolerated in 24 participants completing the protocol. This lower dose was associated with an approximately 60% increase in blood NAD+ levels—a lesser effect than seen with . While blood pressure (BP) was decreased with NR in those with "elevated" blood pressure (systolic BP ≥120mmHg or diastolic BP> 80mmHg), it was unchanged in those with baseline BP <120/80.

#### 1.2 Study rationale

While preliminary data show that oral NR supplementation increases myocardial NAD+ levels in mice, there has been no direct evidence that suggests oral NR increases NAD+

November 18, 2018

levels or improves mitochondrial function in *human* hearts. *Our colleague, [name], currently studies left ventricular myocardial samples obtained from advanced heart failure patients at the time of implantation of left ventricular assist devices (LVADs).* We recently submitted an R01 application (1 R01 HL144937-01) to the NHLBI to test the hypothesis that oral NR supplementation will increase myocardial NAD+ levels and improve cardiomyocyte mitochondrial function in participants with advanced heart failure planned for elective LVAD implantation. The NHLBI CICS Study Section recently reviewed this R01 application, giving it a Priority Score of 42 and a Percentile Score of 24%. However, each of the three Reviewers gave individual review category scores of 1-2 for Significance, Investigator(s), 2-3 for Innovation, but 3-6 for Approach, primarily for lack of preliminary data on feasibility. Therefore, to demonstrate feasibility, we propose to enroll 5 participants planned for LVAD implantation in a Pilot Study of NR in which they will receive NR, up-titrated over 3 days to a final NR dose of 1000mg BID. Blood and myocardial tissue analyses collected previously from age- and gender-matched LVAD recipients will serve as controls. We propose the following Aims:

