# Aim 2: Determine the effect of NR (as compared to historical controls) on NAD(H) levels, mitochondrial function and its regulation through epigenomic modifications in the failing myocardium.

- a. Measure NAD+ and NADH levels in the blood and myocardium of the participants.
- b. Assess mitochondrial morphology and function in cardiac tissue using, respectively, EM and isolated mitochondria.
- c. Determine protein acetylation in the mitochondrial and non-mitochondrial compartments and changes in nuclear gene regulation.

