#### 2. Study Objectives

Enroll 5 participants undergoing elective LVAD placement to study the effects of NR on whole blood and myocardial NAD+ levels, as well as on measures of PBMC and cardiomyocyte mitochondrial function. The effects of NR on blood and myocardial markers of inflammation also will be assessed. Blood and myocardial tissue collected previously from individuals at the time of LVAD implantation will serve as historical controls.

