#### 3. Study design

#### 3.1 Design Overview

This study is a single-center study to compare myocardial NAD+ level and other mitochondrial endpoints from NR administration with baseline untreated patients.

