#### 4.1.2. Exclusion Criteria:

- Current smoking
- Receiving certain concurrent supplements (to be determined at discretion of the PI). Note that UWMC Nutrition Care standards call for a general multivitamin (1 tab PO daily) as part of the advanced heart failure therapy (AHFT) work-up.
- Known allergies to niacin or nicotinamide.
- Hepatic, renal, endocrine, or neurological disease that disqualify them from consideration for LVAD implantation.
- Inability to perform Study visits or procedures.
- Unwillingness/inability to provide informed consent.
- Women who are currently pregnant or who wish to become pregnant over the course of the study follow-up are not allowed to join this study. This exclusion is built into the LVAD candidate selection process.

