## Pre-LVAD implantation Visits (Day 2 or later; starting at least 2 days prior to LVAD implantation surgery)

- Day 2+:
  - Medical history, physical examination, current medical treatments
  - Labs obtained as a part of routine inpatient heart failure clinical care: CBC with WBC differential and platelets, serum chemistry panel (sodium, potassium, chloride, glucose, blood urea nitrogen and creatinine), AST and ALT
  - Record of adverse events, if any
  - Day 3+:
    - Labs obtained as a part of routine inpatient heart failure clinical care: CBC with WBC differential and platelets, serum chemistry panel (sodium, potassium, chloride, glucose, blood urea nitrogen and creatinine), AST and ALT
    - Record of adverse events, if any
    - Subjects then will receive the last 1000 mg dose of NR at 8pm.
- Day 4 (If NOT Day of Surgery):
  - Medical history, physical examination, current medical treatments
  - Labs obtained as a part of routine inpatient heart failure clinical care: CBC with WBC differential and platelets, serum chemistry panel (sodium, potassium, chloride, glucose, blood urea nitrogen and creatinine), AST and ALT
  - Record of adverse events, if any
  - Additional Study blood collection (20mL):
    - 10mL EDTA tube for PBMC isolation
    - 10mL ACD tube for NR and NAD+ assays

(1		(LV	line AD "S luled) Titration ↓ ↑ Daily fro 250→500→1 mg BID	y from Cont. 0→1000 1000		NR Day of	
	Day:	¥ 1	2	¥ Л		▼ (Varia	ble)
		1	2			Pre-O	
	Procedures: History	х	x	х		х	
Safety and Tolerability	Labs	x		X		x	
Salety and Tolerability	Disp Meds	x		x			
Peripheral Blood Effects	NR/NAD+ Levels PBMC Mitochondrial Function			x x		x x	
Myocardial Effects	NAD+/NADH Levels Mitochondrial Function Epigenetic Modifications						x x x
Inflammation/ Inflammasome	Circulating Inflammasome Myocardial Inflammatory Profil	 e				х	x

Day of Surgery

- Medical history, physical examination, current medical treatments
- Routine pre-operative labs
- Additional Study blood collection (20mL):
  - 10mL EDTA tube for PBMC isolation
  - 10mL ACD tube for NR and NAD+ assays
- In the operating room, myocardial samples from the LV apex (removed as an integral part of the LVAD implantation surgery:
  - Flash-frozen in liquid nitrogen for subsequent NAD+/NADH assays
  - Fresh samples for immediate processing for cardiomyocyte mitochondria isolation

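### If control values are taken over from earlier analyses, assay run cannot be separated from NR in the Aim 2 myocardial comparison; the protocol should specify a same-run, coded assay of stored frozen control tissue.

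*Protocol*

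**What the plan says.** The protocol describes the comparator in three ways.

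- Section 1.2: "Blood and myocardial tissue analyses collected previously from age- and gender-matched LVAD recipients will serve as controls".
- Section 2: "Blood and myocardial tissue collected previously from individuals at the time of LVAD implantation will serve as historical controls". No matching is mentioned.
- Section 3.1: the study is to "compare myocardial NAD+ level and other mitochondrial endpoints from NR administration with baseline untreated patients".

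Aim 2 is to "Determine the effect of NR (as compared to historical controls) on NAD(H) levels", together with mitochondrial function and its epigenomic regulation in failing myocardium. One component is: "Assess mitochondrial morphology and function in cardiac tissue using, respectively, EM and isolated mitochondria".

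In Section 6.2, under Day of Surgery, apical tissue is handled in two ways. One portion is "Flash-frozen in liquid nitrogen for subsequent NAD+/NADH assays". Another is processed fresh, at once, to isolate mitochondria. Section 6.3 lists protein acetylation alongside work on frozen material.

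The documents do not give the number of controls, when they were sampled, how long their tissue was stored, or whether any would be assayed again. They do not say whether laboratory staff or image readers know which samples are from NR patients. Section 7 has samples labelled by study number, as a confidentiality measure. The SAP describes a single-arm study with no control group and plans only within-patient, before-and-after tests.

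**The concern.** Blood is drawn before and after NR, so the blood and PBMC measures have a within-patient comparison. Myocardium is not sampled before dosing. Whatever is concluded about NR in the heart comes from NR hearts set against other people's hearts, and Section 11 presents the human myocardium as the main scientific question.

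If the control side consists of results already obtained, any difference in reagents, calibration or operator between runs passes in full into the apparent NR effect. Adding a control comparison to the SAP would not cure this. It has to be dealt with when the samples are assayed and the controls are chosen.

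Two lesser gaps go with it. Electron-microscopy morphology normally involves reader judgement, and no coded reading is described. NR participants are also selected in ways not mirrored for controls: they must be elective cases, Section 4.1.2 excludes "Current smoking", and Aim 1 sets a minimum time at full dose for the primary analysis and a 21-day limit on waiting for surgery.

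**Working it through.** The documents give no sample size calculation, alpha, SD or control number for this comparison, so there is no figure to reproduce. Five participants is a feasibility number (Section 1.2).

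**Step 1. Can NR and run be separated?** Write each myocardial value as

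Y = μ + δ·NR + β·Late + error,

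where NR = 1 for treated hearts and Late = 1 for the later run. If all control values are earlier results, Late = NR for every heart. The three columns (intercept, NR, Late) then have rank 2. Only δ + β can be estimated, and no choice of model separates the two. If all frozen samples are assayed in one run, Late is constant and δ can be estimated, apart from differences in patient selection and storage time.

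**Step 2. Which endpoints are affected?**

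| Endpoint | Material | Section 1.2 wording (analyses) | Section 2 wording (tissue) |
|---|---|---|---|
| NAD+/NADH | Frozen | Run and NR coincide | Same-run assay possible, not specified |
| Protein acetylation | Listed with frozen work | Run and NR coincide | Same-run assay possible, not specified |
| EM morphology | Images | Earlier readings | Coded re-reading possible if images or tissue remain |
| Isolated-mitochondria function | Fresh | Run and NR coincide | Still coincide: fresh historical tissue cannot be re-run |

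**Step 3. How much could a shift matter?** This is illustration only. Assumptions: no true NR effect, two-sided nominal 5%, equal SDs, n = 5 NR hearts, m controls (not given; 5, 10 and 20 tried), and a systematic shift of d SD (not given). The two-sample t statistic is noncentral t with

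df = n + m − 2 and λ = d / √(1/n + 1/m).

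For m = 5 and d = 1: df = 8 and λ = 1/√0.4 = 1.58. The chance of exceeding the two-sided critical value is 28.6%.

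| Shift (SD) | 5 controls | 10 controls | 20 controls |
|---|---|---|---|
| 0 | 5.0% | 5.0% | 5.0% |
| 0.5 | 10.8% | 13.5% | 16.0% |
| 1.0 | 28.6% | 39.4% | 48.3% |
| 1.5 | 54.9% | 71.7% | 81.9% |

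More historical controls make the error worse: they sharpen the estimate of δ + β without removing β. For scale, a true effect would need to be about 2.0 SD with 5 controls, or 1.7 SD with 10, to be detected with 80% power.

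**The case against.** The strongest reply is that this is an openly uncontrolled pilot: "to demonstrate feasibility, we propose to enroll 5 participants planned for LVAD implantation". Aim 1 is enrolment, and the SAP tests nothing against controls, so the percentages above describe a test that nobody has planned. That is fair, and it limits the weight of the point. It does not remove it, because Aims 2 and 3 are still worded as determining an effect and testing a hypothesis against historical controls.

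Several stronger readings are tempting, but the documents do not support them.

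- *The readers were unmasked.* Open label describes treatment. The documents are silent on assay and image readers. Labelling by study number does not prove masking, but silence does not prove its absence. All that can be said is that no masking is specified.
- *Every endpoint is fully confounded with run.* That follows from Section 1.2 as worded, and it holds for fresh-tissue function under either wording. For frozen assays Section 2 leaves a same-run assay open, and it may be what was intended.
- *The controls differ in kind.* Both groups are LVAD recipients sampled at implantation, and Section 1.2 matches them on age and gender. Control eligibility is not described, so differences in smoking, urgency or inpatient status are possible but not shown. The protocol is not uniform on inpatient status for its own participants: Section 4.1.1 requires it, while Section 6.4 provides for people not in hospital at enrolment.
- *A long gap separates the runs.* Section 1.2 says a colleague is currently studying such samples. No dates are given.

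**Conclusion.** The point holds in limited form. The comparator is described inconsistently. Under the Section 1.2 wording, run and NR status coincide in a comparison that has no pre-dose heart sample to fall back on. That is a built-in source of bias for Aim 2, and it can be avoided for the frozen assays. It cannot be avoided for fresh-tissue mitochondrial function with historical controls.

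The size of any bias is unknown. The rates of 11%, 29% and 55% rest entirely on an assumed shift, an assumed 5 controls and a test absent from the SAP. A reader might take them as this trial's false-positive rate; they are not. Nor does the point undermine enrolment, safety review or the paired blood and PBMC analyses. It limits what can be concluded about NR in myocardium, and the change is worth making because it is cheap.

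**What to change.** 1. Reword Section 1.2 to agree with Section 2, and bring Section 3.1 into line, so that the control source is stated once.
2. State that, where stored frozen control tissue remains, it will be assayed for myocardial NAD+/NADH and protein acetylation in the same run as the NR samples, interleaved and under random codes.
3. State that EM images from both groups will be read under the same codes.
4. Choose controls before the new assay results are seen, from recipients who also meet those Section 4.1 criteria that can be checked in their records. Report how many were available and used.
5. Report fresh-tissue mitochondrial function against historical controls as descriptive and not batch-controlled. Note storage time as a difference that remains even after a same-run assay.

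The cost is reagents, some banked tissue, the work of coding tubes and images, and possibly fewer eligible controls. Samples from early NR participants would also have to be held until the joint run. No extra patient procedure is needed. Items 2 and 3 depend on control tissue and images still being available, which the documents do not confirm. If they are not, the myocardial comparison should be reported as descriptive throughout, with the assay run of each group stated.

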## Aim 1: Enroll 5 participants scheduled for elective LVAD placement into an open-label study of NR.

a. Participants will have labs (including safety panels) drawn at baseline (Day 1), then receive escalating doses of NR to a maximum dose of 1000mg twice daily by Day 3. Participants will be continued on NR at 1000mg twice daily until LVAD implantation surgery.

On the morning of LVAD implantation Surgery (Day 5 or later), participants will have final labs drawn. Samples of fresh cardiac tissue removed from the left ventricular apex during LVAD implantation surgery will be collected in the operating room. The primary analyses will be performed on NR-treated participants who were on the maximum NR dose of 1000mg twice daily for at least 2 days prior to LVAD implantation surgery. We will cap the maximum day of NR administration to 21 days. If the surgery doesn't happen by then, we will exclude the patient from the study.

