# Aim 3: Test the hypothesis that NR improves mitochondrial function and reduces inflammatory response in HF patients receiving NR (as compared to historical controls).

- a. Measure mitochondrial function in peripheral blood mononucleated cells (PBMC).
- b. Determine the inflammatory response in PBMC.
- c. Compare effects on the circulating inflammasome vs. myocardial inflammation.

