#### 5. Treatments

At the AHFT Thursday meeting, if the committee decides that a participant is to receive an LVAD, he or she will be prescribed NR according to the following administration schedule: Dose Escalation

Day 1: 250 mg (1 capsule) twice daily (total daily intake = 500 mg)

Day 2: 500 mg (2 capsules) twice daily (total daily intake = 1000 mg)

Day 3: 1000 mg (4 capsules) twice daily (total daily intake = 2000 mg)

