#### Dose Maintenance

Day 4: 1000 mg (4 capsules) twice daily

Day 5-21 as applicable thru Day Before Surgery: 1000 mg (4 capsules) twice daily

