#### Washout

Day of LVAD Surgery and/or Day 22: None

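### Aim 1 excludes from the study any dosed participant not operated on by the 21-day cap, and neither document keeps that person in safety reporting, DSMB review or the participant count

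*Protocol*

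**What the plan says.** - **The rule.** Protocol section 1.2, Aim 1, sets a 21-day limit on NR and says that if surgery has not taken place by then "we will exclude the patient from the study".
- **The primary analysis set.** Earlier in the same paragraph, the primary analyses are limited to treated participants who were "on the maximum NR dose of 1000mg twice daily for at least 2 days prior to LVAD implantation surgery".
- **The case is foreseen.** The washout line in section 5 reads "Day of LVAD Surgery and/or Day 22: None". Section 6.2 provides for discharge home with up to 7 days of study drug when surgery is delayed.
- **Safety collection.** Section 6.2 has discharged participants telephoned every day. Section 6.4 adds an interview 4 weeks after the last dose, timed from dosing and not from surgery. Section 7 covers storage of the data.
- **Safety review.** Section 12 has the DSMB review safety once each of the five planned NR recipients has completed the study.
- **Purpose.** Section 1.2 says that "to demonstrate feasibility, we propose to enroll 5 participants planned for LVAD implantation".
- **SAP.** The plan compares blood and PBMC measures before and after NR in every study subject. It defines no analysis set, does not say which draw counts as after, and has no rule for participants excluded at the cap.

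**The concern.** The object of the exclusion is the study, not the tissue analysis. Whether surgery happens within 21 days is known only after NR has started, so the rule makes membership of the reported group depend on a post-treatment event. That is harmless for analyses that cannot be done without surgery. It is not harmless for safety, which can be described for anyone who took a capsule, or for the number of people dosed.

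In an open-label pilot of five, each dosed person is 20% of the planned sample. The pilot exists to show feasibility, and a participant who was dosed but not operated on in time bears directly on that. If such a person disappears from the report, a reader cannot tell how many were treated or what happened to all of them.

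**Working it through.** **1. Which analyses need surgery?**

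| Item | Needs surgery? | Source |
|---|---|---|
| Primary analyses | Yes, already restricted by "on the maximum NR dose of 1000mg twice daily for at least 2 days prior to LVAD implantation surgery" | Section 1.2, Aim 1 |
| Myocardial NAD(H), mitochondria, acetylation | Yes | Aim 2 |
| "Compare effects on the circulating inflammasome vs. myocardial inflammation" | Yes | Aim 3 |
| Blood-myocardium correlations | Yes, surgical samples | Section 11 |
| Historical-control comparisons: "Blood and myocardial tissue collected previously from individuals at the time of LVAD implantation will serve as historical controls" | Yes, to match the controls' time point | Section 2 |
| Before-after blood and PBMC test | Unclear, because the after draw is not named | SAP; section 6.2 has draws on Day 4 and on the day of surgery |
| Safety, DSMB review, count of dosed participants | No | Sections 6.2, 6.4, 12 |

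The existing restriction, or the absence of tissue, already settles the rows marked yes. What the exclusion sentence adds falls on the last row, and possibly on the blood test.

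**2. Does another passage keep the data?** Sections 6.2, 6.4 and 7 deal with collection and storage and say nothing about reporting. Section 12 refers to participants receiving NR, but its trigger is completion, which a person excluded from the study may never reach. The SAP's reference to every study subject does not say whether an excluded person is still one. No passage settles it.

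**3. How much exposure could be dropped?** The inputs are the section 5 schedule: "Day 1: 250 mg (1 capsule) twice daily (total daily intake = 500 mg"), then 1000 mg in total on Day 2, 2000 mg in total on Day 3, and "Day 5-21 as applicable thru Day Before Surgery: 1000 mg (4 capsules) twice daily", with none on the day of surgery. Full adherence is assumed.
- Dosed to the cap: 500 + 1000 + 19 × 2000 = 39,500 mg over 21 days.
- Surgery on Day 5, the earliest day in Aim 1: 500 + 1000 + 2 × 2000 = 5,500 mg over 4 days.
- Ratio: 39,500 / 5,500 = 7.2.

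Share of all dosing days removed if one of five is excluded after the full 21 days:
- other four operated on Day 5: 21 / (4 × 4 + 21) = 57%
- other four operated on Day 10: 21 / (4 × 9 + 21) = 37%
- other four also dosed for 21 days: 21 / (4 × 21 + 21) = 20%

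**4. Can an excluded participant have less exposure than a retained one?** Yes. Suppose discharge on Day 4 with a 7-day supply and no readmission: 4 + 7 = 11 dosing days. A retained participant operated on Day 20 has 19. If all four others had 19, the share removed is 11 / (4 × 19 + 11) = 13%.

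**5. How likely is it?** The documents give no rate. If the chance of missing the cap is assumed to be 5%, 10%, 20% or 30% per participant, the chance that at least one of five is excluded, 1 − (1 − q)^5, is 23%, 41%, 67% or 83%.

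**6. Effect on a safety statement, for scale.** With zero events of a given type, the one-sided 95% upper bound 1 − 0.05^(1/n) is 45% for n = 5 and 53% for n = 4, assuming no replacement. Neither is tight.

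**The case against.** The strongest reply is that exclusion may only mean that participation ends. The interview is timed from the last dose, the schedule provides for Day 22, section 12 speaks of participants receiving NR, and section 4.3 says study IDs are never re-used, which leaves an enrolment trail. All of this fits an intention to keep the data. It stands as a possible reading, but none of it says that the data are reported, and the literal wording points the other way.

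Three stronger readings are tempting, and the documents do not support them.

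- *The excluded participants are necessarily the most exposed.* The trigger is no surgery by the cap, not dosing up to the cap. Step 4 shows that an excluded person can have less exposure than a retained one, so the 57%, 37% and 20% figures describe only someone dosed for all 21 days.
- *The before-after blood test is needlessly weakened.* Going from five pairs to four would widen the 95% half-width of a mean change from 2.776/√5 = 1.24 to 3.182/√4 = 1.59 SD. That loss is avoidable only if Day 4 blood counts as an after draw, which the SAP does not say. Day 4 also reflects only about one day at maximum dose, so leaving non-operated participants out of the main blood test is defensible.
- *A result of 4 out of 5 reaching surgery would be published as 4 out of 4.* No feasibility rate or reporting rule is defined. The documents permit that outcome but do not predict it.

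**Conclusion.** The point holds for safety reporting, DSMB review and the count of dosed participants, and no further. As written, the rule removes a treated person from the study for a post-treatment reason, the primary analyses do not need it to, and no other passage brings the person back.

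The size is one participant in five for each exclusion, with up to 21 dosing days and 39,500 mg if adherence is full, but possibly much less. The exposure shares and zero-event bounds are illustrations. They rest on assumed surgery dates, full adherence and, for the bounds, no replacement. The documents give no frequency for reaching the cap, no replacement rule and no reasons for delay, so the direction of any bias is unknown. Biased efficacy results should not be inferred from this rule. It is a gap in a stated rule that should be closed, and closing it is cheap.

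**What to change.** Replace the last sentence of Aim 1 in section 1.2 with wording such as:

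> If surgery has not occurred by then, the participant is excluded only from analyses that need tissue or surgery-day samples: myocardial endpoints, blood-myocardium correlations, the circulating-versus-myocardial comparison, and comparisons with historical controls. Every participant who received at least one NR dose remains in the safety reporting, the DSMB review, and the reported count of participants who did and did not reach surgery.

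Align section 12 so that completion of the study, as the trigger for DSMB review, includes participants excluded at the cap.

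Optional: if Day 4 blood is accepted as an after draw, show the Day 1/Day 4 pair of these participants in a sensitivity analysis. The SAP template already reports a paired result for PBMC maximal respiration (p = 0.0405), so an analysis added after that must be labelled post hoc. It would not restore precision in the main test.

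The cost is wording only. The Day 4 draw, the daily calls to discharged participants and the 4-week interview are already planned, so no visit or sample is added. The dosing cap is left as it is.
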